Participants will also complete a demographic, sexual behavior, and drug use questionnaire (Enrollment survey), and physical exam findings will be abstracted from the medical record if appropriate.

For the randomized group, in addition to SOC testing, participants will also be randomized to either undergo HIV VL POC testing (Cepheid GeneXpert HIV-1 Viral Load (Xpert VL; Cepheid, Sunnyvale, CA)) using blood already collected or receive SOC testing only. . Those in the non-randomized group will all undergo the Cepheid GeneXpert HIV-1 Qual test, if resources allow. If resources do not allow, the non-randomized group will undergo all standard HIV diagnostics without the HIV VL POC test. Those with confirmed HIV infection will be referred to their preferred clinician, and to the local Disease Intervention Specialist (DIS) team for linkage to care and partner services. Those with non-reactive/negative test results will be referred to their preferred clinician for consideration of HIV PrEP and prevention counselling.

Participants will receive an HIV VL result from the Johns Hopkins Molecular virology lab within 24 hours (same day) using either a validated FDA approved or a validated result from a research use only test performed in a CLIA-licensed lab. Only the results of FDA-approved testing or validated result from a research use only test performed in a CLIA-approved lab may be shared with participants. We will collect blood and transfer the sample to the Immunology Laboratory at JHH for testing. Participants will be contacted within 1 working day of results being released to clinical staff and referred to HIV prevention or treatment services. For the randomized group, in order to ensure that contact details are up-to-date and to proactively answer any participant questions we will contact participants between the 4- and 12-week visits by telephone, SMS, or email as previously agreed.

At Week 4 Visit (all participants – email and/or telephone call)

Participant: Questionnaires: HIV symptom and care; behavioral survey. Linkage to care information. Change in medication. Results of interval laboratory tests.

Study Team (abstraction from medical record): Participant symptoms, physical exam findings. Linkage to care information. Change in medication. Results of interval laboratory tests.

At Week 12 Visit (participants in randomized group only)

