Participant: Questionnaires (using REDCap to be completed on site or through email as previously agreed): HIV symptom and care; behavioral survey. Provide oral fluid (e.g. in DPP samplertainer) – to be processed and frozen for storage in the biorepository and future lab evaluation of HIV and syphilis at the CDC. Linkage to care information. Change in medication. Results of interval laboratory tests.

Study Team (abstraction from medical record): Participant symptoms, physical exam findings. Linkage to care information. Change in medication. Results of interval laboratory tests.

Laboratory tests: HIV RNA testing – qual (batched) / quant (real time) – on everybody

For participants with discordant Chembio DPP Syphilis results when compared with reverse algorithm syphilis serological testing results at enrollment, both tests will be repeated.

Off-Study

Randomized group:

- After the completion of the 12-week visit, participants in the randomized group will be followed for an additional 30 days to monitor for any adverse events from the blood draw and any relevant outcomes (e.g. linkage-to-care). After this 30-day period, participants will be considered off-study and will no longer be followed.
- For participants who do not complete the 12-week visit, after the eligibility window for the visit has passed, participants in the randomized group will be followed for an additional 30 days to monitor for any relevant outcomes (e.g. linkage-to-care). After this 30-day period, participants will be considered off-study and will no longer be followed.

Non-randomized group:

- After the completion of the 4-week visit, participants in the non-randomized group will be followed for an additional 30 days to monitor for any relevant outcomes (e.g. linkage-to-care). After this 30-day period, participants will be considered off-study and will no longer be followed.
- For participants who do not complete the 4-week visit, after the eligibility window for the visit has passed, participants in the non-randomized group will be followed for an

additional 30 days to monitor for any relevant outcomes (e.g. linkage-to-care). After this 30-day period, participants will be considered off-study and will no longer be followed.

Sample storage

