- 2) They have two consecutive study visits with non-reactive/negative results for all tests (indicating tests that had false-reactive/positive results), or
- 3) They complete follow up out to 70 days after the initial visit (Day 0).

The follow-up schedule will include return visits at 3, 7, 10, 14, 21, 28, 42, 56, and 70 days after the initial visit (i.e., the day of Study participation or Day 0). At each follow-up visit, participants will provide blood (via venipuncture) and oral fluid specimens for storage and testing with the HIV POC tests under evaluation (e.g., OraQuick, DPP HIV/syphilis); other laboratory HIV diagnostics where applicable and HIV RNA Quant and HIV RNA Qual as well as complete a HIV symptom and care questionnaire. Linkage to care information. Change in medication. Results of interval laboratory tests.

Day 0 – enrollment

Day 3 (window minus 1 day to plus 2 days)

Day 7 (window minus 1 day to plus 2 days)

Day 10 (window minus 1 day to plus 2 days)

Day 14 (window minus 1 day to plus 3 days)

Day 21 (window minus 3 day to plus 3 days)

Day 28 (window minus 3 day to plus 7 days)

Day 42 (window minus 7 day to plus 7 days)

Day 56 (window minus 7 day to plus 7 days)

Day 70 (window minus 7 day to plus 14 days)

d. Blinding, including justification for blinding or not blinding the trial, if applicable.

For the randomized group, participants will be randomized to receive either a POC HIV VL test or usual clinical care. It will not be possible to blind participants or the research team to this intervention. The participant and their clinician will be informed of the POC HIV VL result.

e. Justification of why participants will not receive routine care or will have current therapy stopped.

All participants will receive routine clinical care. The study will provide additional assessments to routine care and will not replace any element of routine care. There is no implication for changes in participant's current therapy.

f. Justification for inclusion of a placebo or non-treatment group.

There is no placebo group. Treatment is not a component of this study. For the randomized group, participants will be randomized to receive an additional HIV POC VL test that is not currently used in clinical practice in Baltimore to diagnose HIV infection and to guide referral for rapid ART initiation or HIV PrEP. There is sufficient equipoise to justify use of HIV POC VL testing.

g. Definition of treatment failure or participant removal criteria.

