To maximize recruitment efforts and facilitate access to research to the broadest possible community, we will invite members of the public to consider joining the study. We will target key populations, including PrEP users, MSM, and transgender people through outreach to trusted community-based organizations (CBOs). Information will be made available through social media and more traditional methods, such as posters and flyers. Individuals who contact the study team expressing an interest in the study will be invited to the ICTR CRUs.

Prior to study enrollment, the study team will confirm that people who are recruited via non-clinic venues have a medical provider who can be contacted with the results of positive study laboratory results. If a participant does not have a provider, the study team will confirm that they are willing to be referred to an appropriate provider for care and treatment.

Venue for follow up visits and sample collection

Study participants who are recruited from the non-clinical sites described above will be asked to come to the ICTR-CRUs. Similarly, for those with discordant HIV results (recruited from any location) will attend the CRU, Bartlett Clinic, and BCHD for their follow up visits.

7. Drugs/ Substances/ Devices:

- a. The rationale for choosing the drug and dose or for choosing the device to be used.

In this study, we will be testing performance of point of care (POC) devices, Chembio DPP HIV-Syphilis and OraQuick Advance HIV test, for rapid detection of HIV and Syphilis antibodies. Participants in the intervention (POC) arm will also receive nucleic acid amplification test for HIV viral load quantification using Roche Cobas HIV-1 Realtime PCR test and/or Cepheid GeneXpert HIV-1 viral load test.

We acknowledge in-kind contribution (non-monetary support), as Roche Diagnostics and Cepheid have agreed to provide test kits (cartridges) for this study.

- b. Justification and safety information if FDA approved drugs will be administered for non-FDA approved indications or if doses or routes of administration or participant populations are changed.

NA

- c. Justification and safety information if non-FDA approved drugs without an IND will be administered.

NA

8. Study Statistics:

- a. Primary outcome variable.

Proportion of participants linked either to PrEP or ART

- b. Secondary outcome variables.

Syphilis: linkage to syphilis treatment and time to linkage

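### Section 5.d leaves the whole research team unblinded and does not exempt outcome assessment, so linkage, the sole primary outcome, could be recorded or classified differently by arm

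*Combined protocol and SAP*

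**What the plan says.** - **Blinding (section 5.d).** "It will not be possible to blind participants or the research team to this intervention". The same paragraph adds: "The participant and their clinician will be informed of the POC HIV VL result". No exception is made for outcome assessment.
- **Primary outcome (section 8.a).** "Proportion of participants linked either to PrEP or ART". Neither here nor in the schema notes in section 5.a does the plan give a qualifying event, a time point, or a rule for when sources disagree.
- **Source 1, participant report.** At week 4, by email and/or telephone: "Participant: Questionnaires: HIV symptom and care; behavioral survey. Linkage to care information". The week 12 questionnaire asks for linkage again, through REDCap on site or by email.
- **Source 2, records.** At weeks 4 and 12: "Study Team (abstraction from medical record): Participant symptoms, physical exam findings. Linkage to care information". Under the Off-Study heading, monitoring for linkage continues for a further 30 days.
- **Who knows the arm.** Under the Randomization heading, research staff carry out the randomization.
- **Contact and referral (section 5.a, at enrollment).** "Participants will be contacted within 1 working day of results being released to clinical staff and referred to HIV prevention or treatment services". The role that does this is not named. Preferred clinicians receive referrals, and for participants with HIV so does the Disease Intervention Specialist team.

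The plan describes no masked abstractor, no adjudication and no separation of roles.

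**The concern.** Section 5.d gives one reason for an open trial: the intervention cannot be hidden. That reason covers the people who receive the test result, act on it or deliver the test. It does not cover the later step of reading collected information and coding linked or not linked, with a date. That step can be done without the arm.

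Masking matters most when an outcome leaves room for judgement, and this one does. Linkage is undefined, part of it is self-reported, and part depends on how hard someone looks in the record. Section 6 lists emergency departments, a specialty practice, city clinics, referrals from a network of more than 40 locations, and recruitment from the public. Evidence of linkage may therefore be scattered, and search effort can change what is found. Staff who know the arm could follow up an ambiguous entry, or accept an unconfirmed report, more readily in one arm.

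At stake is the primary comparison, and also the Cox model for time to linkage in section 8.c, which needs the linkage date. Only differences in recording or classification count as bias. Linkage that truly happens because a result arrived sooner is part of the intervention effect.

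**Working it through.** **Inputs.** From section 8.c: 40% linkage under standard of care, 55% with the POC test, two-sided 0.05, power 80%, 173 per arm, and 204 per arm after 15% non-response. The documents give no misclassification rates, so the gaps in step 2 are assumptions.

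**Step 1: the plan's own figure.** With p1 = 0.40, p2 = 0.55, mean p = 0.475 and pooled variance under the null:

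n = [1.960 × √(2 × 0.475 × 0.525) + 0.842 × √(0.40 × 0.60 + 0.55 × 0.45)]² / 0.15² = 172.8, rounded up to 173.

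173 / 0.85 = 203.5, rounded up to 204. Both figures reproduce. Masked classification would not alter either.

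**Step 2: what a spurious gap does when there is no true effect.** True linkage is 40% in both arms, with 173 evaluable per arm. One arm is recorded at 40% and the other at 40% + d. With p the mean of the two recorded proportions:

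- SE0 = √(2p(1 − p)/173)
- SE1 = √([p1(1 − p1) + p2(1 − p2)]/173)
- Rejection rate = Φ((d − 1.960 SE0)/SE1) + Φ((−d − 1.960 SE0)/SE1)

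| Recorded proportions | d | SE0 | SE1 | Upper tail | Lower tail | Rejection rate |
|---|---|---|---|---|---|---|
| 40% v 40% | 0 | – | – | 2.5% | 2.5% | 5.0% |
| 40% v 43% | 3 points | 0.0530 | 0.0530 | 8.2% | 0.6% | 8.7% |
| 40% v 45% | 5 points | 0.0532 | 0.0531 | 15.4% | 0.2% | 15.6% |
| 40% v 47% | 7 points | 0.0533 | 0.0532 | 25.8% | 0.1% | 25.9% |

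Tails are rounded separately. Exact binomial enumeration gives 8.8%, 15.4% and 25.4% for the three gaps, so the normal approximation is adequate.

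**Step 3: how much miscoding each gap needs.** If 60% of an arm is truly unlinked and all the error is over-counting in that arm, the share miscoded is d/60:

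- 3 points: 3/60 = 5%
- 5 points: 5/60 = 8.3%
- 7 points: 7/60 = 11.7%
- the full planned 15 points: 15/60 = 25%

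Missed linkages in one arm act the same way. Missing 10% of true linkages there records 36% against 40% and gives a rejection rate of 11.9%.

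**Step 4: which roles need the arm.** Participants and clinicians are told the result, and staff delivering the test must know the arm. No procedure in the plan requires the arm at the point where linkage is coded.

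**The case against.** **Same staff.** A reader might infer that the staff who make the referrals also decide who was linked. The documents do not say so. Referral is in the passive voice, clinicians and the Disease Intervention Specialist team take part, and no classifier is named. What stands is narrower: the roles are not separated.

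**Staff contact.** The contact between weeks 4 and 12 might look like an arm-dependent outcome interview. Its stated purpose includes "to proactively answer any participant questions we will contact participants between the 4- and 12-week visits by telephone, SMS, or email as previously agreed", along with keeping contact details current. It covers the whole randomized group and is not an outcome assessment. Referral also occurs in both arms.

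**Self-completion.** Section 8.f describes computer-assisted self-interviews, and week 12 uses REDCap. Staff probing is plausible mainly for the week 4 telephone option. This limits influence on self-report but leaves chart abstraction untouched.

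**Size and direction.** A tendency to favour the POC arm is plausible, but the documents do not establish it, and a 7-point gap needs considerable one-sided error. This objection stands, so the figures above are illustrations and not estimates.

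**Record-only linkage.** Making this the primary outcome could introduce its own bias. Participants may go to preferred or outside clinicians, and if that differs by arm, missed records would differ too. This also stands and narrows the fix.

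**Limits of masking.** Removing the arm from an extract masks classification but not the search. Because clinicians are told the POC result, it may also appear in the notes. Both limits are real.

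**Conclusion.** The concern holds as an avoidable weakness in design. Section 5.d declares the whole research team unblinded without exempting outcome assessment. An undefined primary outcome is then collected from self-report and from that team's own chart abstraction, with nothing to keep coding independent of arm.

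The documents do not support a claim that bias will occur, that it must favour the POC arm, or that nothing could be done about it afterwards. Records are collected in both arms, so a record-confirmed analysis remains possible, although it cannot undo an unequal search.

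The rejection rates of 8.7%, 15.6% and 25.9% rest on three assumptions: no true effect, 40% linkage in both arms with 173 evaluable per arm, and a spurious excess of 3, 5 or 7 points confined to one arm. Small differential errors raise the type I error modestly. They would not on their own produce the planned 15-point difference. The change is worth making because it is cheap now and the trial is meant to inform HIV testing guidelines.

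**What to change.** 1. **Section 5.d.** Limit the statement to participants, treating clinicians and staff delivering the test. State that linkage will be classified without knowledge of the arm.
2. **Section 8.a.** Prespecify one linkage rule: the qualifying dated event, the time point, and how self-report and records combine when they differ.
3. **Section 5.a.** Use the same record sources and the same search checklist in both arms.
4. **Section 8.f.** Derive linked or not linked, and the date, from an extract with the arm and POC viral load fields removed. Lock the result before the arm code is merged.
5. **Section 8.c.** Add a sensitivity analysis counting only record-confirmed linkage. Do not make record-only linkage the primary outcome.

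**Cost.** Protocol wording and a small data-management step. Abstraction is already planned. The de-identified data described in section 8.f are for submission to CDC, so the masked extract is an additional product. The numbers stay at 173 evaluable and 204 enrolled per arm. The search itself remains unmasked, so the identical-search rule is what limits unequal chart searching.

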Treatment failure is not a component of this study.

Participants who provide consent and are enrolled, but who do not provide biological samples will be classified as early withdrawals.

Voluntary Withdrawal by a Participant: Participants may withdraw voluntarily from study participation at any time. Participants who withdraw will continue their care with the appropriate clinical service for evaluation and care.

h. Description of what happens to participants receiving therapy when study ends or if a participant's participation in the study ends prematurely.

NA. Treatment is not a component of this study.

i. If biological materials are involved, please describe all the experimental procedures and analyses in which they will be used.

Blood samples:

Blood:

- POC HIV and syphilis testing (DPP HIV-Syphilis System) – whole blood
- Plasma: POC HIV VL testing (Cepheid GeneXpert or comparable platform)
- Plasma: Reference laboratory-based HIV diagnostic (Roche Elecsys with reflex to Geenius and Roche cobas quantitative HIV-1 RNA tie-breaker) and HIV RNA testing (Roche cobas qualitative and quantitative test) as appropriate. Plasma remaining after HIV diagnostic testing will be retrieved by study staff and used for IRB-approved testing, and biorepository storage. All Roche cobas qualitative tests will be run retrospectively on frozen plasma with batched testing.
- Remnant blood collected from a random subset of participants (up to N=100) may be spotted on Plasma Separation Cards, stored and then processed. Results will be compared against SOC plasma HIV RNA viral load tests to determine the sensitivity of POC viral loads tests at varying levels of viremia.
- Serum: reference lab-based testing for treponemal antibody testing, and, if positive, RPR titer. Serum remaining after treponemal antibody testing will be retrieved by study staff and stored in the research laboratory for IRB-approved testing, and biorepository storage.

- For storage for testing with future HIV or syphilis assays

Oral fluid:

- OraQuick HIV antibody testing
- For storage for testing with future HIV assays (e.g., using the Chembio DPP sampletainer)

Randomization:

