For participants in the randomized group, all eligible consented participants will be randomized to receive one of two testing arms using a computerized randomization system in the ratio of 1:1. Participants will be randomized to receive either POC HIV VL plus SOC testing or SOC testing only. Randomization will be performed by research staff after informed consent and verification of all eligibility criteria have been performed.

Early Withdrawals:

Participants who have provided consent and are enrolled, but who do not complete all study procedures at the time of enrollment, will be removed from the study and classified as early withdrawals. Participants may also be removed from the study early for failing to follow instructions, if continuation is deemed potentially harmful, or for any other reason at the discretion of the study principal investigator.

6. Study sites:

The following study sites are planned for the conduct of this study.

1. Johns Hopkins Medicine Emergency Department (JHMED)
2. The John G. Bartlett Specialty Practice (JGBSP), Johns Hopkins Hospital
3. The Baltimore City Health Department (BCHD) Health and Wellness Center, Sexual Health Clinics

These sites have been selected to provide optimal settings for patient interaction, and to provide access to patients at high risk of HIV infection.

Potential participants may be seen at any of the sites mentioned below or the Clinical Research Units (CRU) at the Institute for Clinical and Translational Research (ICTR).

Johns Hopkins Hospital Emergency Department (JHHED) is located in East Baltimore, Maryland. (Drs. [name] and [name]). The mission of JHHED is to provide a patient-centered care experience by world-class emergency health care providers. The JHH ED serves a predominantly socioeconomically-disadvantaged population in the metropolitan area with 60% from Baltimore City, one of the localities hardest hit by the HIV epidemic and 33% from Baltimore County. JHH adult ED patient population is comprised of 15% previous or current injection drug users, with a high prevalence of sexually transmitted infections (STIs) [21-23] and 6% HIV seroprevalence[24]. In FY 2022, the JHH ED had approximately 60,000 adult patient visits. Of these, approximately 65% of the patients were Black or African American and 5% had previously-diagnosed HIV

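### The removal rule permits exclusions after randomization in an open-label trial, and no intention-to-treat set or denominator is specified to protect the primary comparison

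*Combined protocol and SAP*

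**What the plan says.** All references are to the combined protocol and SAP.

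- **Section 5, Early Withdrawals.** Participants who have consented and enrolled but "who do not complete all study procedures at the time of enrollment, will be removed from the study and classified as early withdrawals". The next sentence allows early removal "for failing to follow instructions, if continuation is deemed potentially harmful, or for any other reason at the discretion of the study principal investigator". No exception is made for randomized participants, and the discretionary clause has no time limit.
- **Section 5, Randomization.** "Randomization will be performed by research staff after informed consent and verification of all eligibility criteria have been performed". Completing the enrollment procedures is not a precondition for allocation.
- **Section 5.d, Blinding.** "It will not be possible to blind participants or the research team to this intervention".
- **Section 5.g, removal criteria.** Early withdrawal is described more narrowly: enrolled participants "who do not provide biological samples will be classified as early withdrawals". Removal is not mentioned there.
- **Section 5, Study Procedures.** In the randomized group the POC viral load test is run in one arm only, "using blood already collected or receive SOC testing only" being the wording that describes the two options.
- **Section 8.a to 8.c.** The primary outcome is the proportion linked to PrEP or ART. No denominator, analysis set or intention-to-treat principle is given, and nothing is said about removed participants. The multivariable regression for linkage takes having the POC viral load test as its exposure. The Cox model for time to linkage is by study arm.

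**The concern.** A randomized comparison is protected only if the people analysed are the people allocated. Here one clause requires removal for incomplete enrollment procedures, another leaves removal to the judgment of someone who can know the arm, and the statistics section does not say that removed participants stay in the analysis.

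People who leave before finishing the Day 0 tasks are plausibly less likely than average to link to care. If more of them were removed from one arm, and the analysis used only those remaining, that arm's linkage proportion would rise without any true effect. Describing the main regression by test received rather than by arm allocated leaves the same gap: someone allocated to POC who did not get the test has no clear place in the analysis.

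If removal also stops the collection of linkage data, the outcome may not be recoverable later. This is the primary outcome of a trial meant to inform national HIV testing guidance.

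**Working it through.** **1. The plan's own sample size (section 8.c).** Inputs: 40% v 55% linked, two-sided 0.05, 80% power, 15% non-response, 1:1 allocation. With a pooled-variance normal approximation and mean proportion 0.475:

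n = [1.96 × √(2 × 0.475 × 0.525) + 0.8416 × √(0.40 × 0.60 + 0.55 × 0.45)]² / 0.15² = 172.8, so 173 per arm.

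173 / 0.85 = 203.5, so 204 per arm. Both figures in the plan are reproduced. The 204 is thus sized to leave 173 responders per arm; it does not say how the other 31 enter the primary proportion.

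**2. Bias if removed participants are left out.** The documents give no removal rates, so those below are assumptions. Take no true effect, 40% linkage among all randomized in both arms, and 204 per arm. With removed share r and linkage q among those removed, the proportion linked among those remaining is

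p = (0.40 − r × q) / (1 − r), with n = 204 × (1 − r).

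Worked case, 10% v 2% removed and q = 0: POC 0.40 / 0.90 = 44.4% (n = 183.6); SOC 0.40 / 0.98 = 40.8% (n = 199.9); difference +3.6 points. The standard error is about 0.0505, so the two-sided rejection probability is 0.107 + 0.004 = 0.111.

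| Removed, POC v SOC | Linkage among removed | Spurious difference | Two-sided type I error |
|---|---|---|---|
| Equal, e.g. 10% v 10% | 0% | 0 | 5.0% |
| 3% v 2% | 0% | +0.4 points | 5.1% |
| 4% v 2% | 0% | +0.9 points | 5.3% |
| 10% v 2% | 20% | +1.8 points | 6.5% |
| 10% v 2% | 0% | +3.6 points | 11.1% |
| 15% v 5% | 0% | +5.0 points | 15.9% |

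The distortion needs removal that is both unequal between arms and related to linkage. With a small gap it is minor.

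**3. Power if all 204 per arm are analysed.**

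- If the planned 15% non-responders all count as not linked: 0.85 × 0.40 = 34% v 0.85 × 0.55 = 46.75%, power 74.9%.
- If every outcome is recovered and 40% v 55% holds: power 86.1%.

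**The case against.** The strongest reply is that the documents do not state the damaging step. A reader might infer that removed participants are dropped from the analysis and that the comparison is therefore not intention-to-treat. The text says removed from the study; no sentence in section 8 excludes them from the primary analysis, and the Cox model is by study arm. That reply stands. What can be said is that intention-to-treat is unspecified and that the rule as written could undermine it.

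A reader might also infer that the rule is stricter in the POC arm because that arm has one more test. This is not established. The test uses blood already drawn, the tasks asked of participants at Day 0 are listed for everyone, and nothing says that an unrun laboratory test makes the participant a non-completer. The same wording suggests that blood may be drawn before allocation, so some non-completers may never be randomized. The order is not fixed either way.

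Three further points stand:

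- The open-ended discretion belongs to the principal investigator, not to staff at large.
- Eligibility already requires willingness to give samples and complete the questionnaire, which should keep removals few.
- The two early-withdrawal descriptions are not a clear contradiction. People who give no samples are a subset of those who do not complete every procedure.

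One reply stands only in part. The Off-Study text keeps following randomized participants for linkage after a missed week 12 visit, which shows that outcomes can be obtained without a visit. It does not mention people removed under Early Withdrawals.

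**Conclusion.** The concern holds in a limited form. The protocol requires or allows removal after allocation, with the arm known, and the statistical section contains nothing that keeps removed participants in the primary comparison. Following the plan as written therefore permits exclusions that can bias the result; whether they would occur, or differ by arm, cannot be told from the documents.

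The size depends wholly on assumed removal rates. With no linkage among those removed it runs from +0.9 points and 5.3% type I error at 4% v 2%, to +3.6 points and 11% at 10% v 2%, and is nil under no true effect when removal and linkage among the removed are equal in both arms. The larger figures should not be read as a forecast. The case for acting is that the gap touches the primary outcome, costs little to close, and may not be repairable if linkage data are not collected after removal.

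**What to change.** Change sections 5 and 8 as follows:

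1. State that every randomized participant is analysed in the allocated arm, and define the exposure in the main regression as allocated arm.
2. State that removal or incomplete procedures end study procedures only. Linkage continues to be abstracted from the medical record unless consent is withdrawn.
3. Count participants with no evidence of linkage as not linked in the primary analysis, with a responders-only sensitivity analysis.
4. Report removals by arm, with reasons and timing relative to allocation.
5. Restate power for 204 per arm analysed: about 75% if the planned 15% non-responders all count as not linked, and up to 86% if every outcome is recovered and 40% v 55% holds.
6. Align the early-withdrawal descriptions in section 5.g and under Early Withdrawals.

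The cost is protocol wording, record abstraction for a few more people, and possibly a lower stated power. The planned number of participants need not change.
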